9.6.3.3 Physical examination

Part 1 (CHICO)

Physical examinations will be performed by a medically qualified person. A complete physical examination of body systems will be performed at the Screening Visit. A brief physical examination, including assessments of heart, lungs, and abdomen, skin for the presence of severe dermatitis, and assessments for the presence of peripheral neuropathy will be performed at all subsequent designated time points (see Table 9–1). Abnormal findings on physical examination at Screening will be documented as medical history; abnormal findings thereafter will be documented as AEs (see Section 9.6.1.1).¹⁷³

A neurological examination will be performed at Screening, and Visits 3, 6, and 8 (EOT). The examination will include assessments of mental status and cognition, cranial nerves, motor function, deep tendon reflexes, sensation, and coordination and gait. Abnormal findings on neurological examination at Screening will be documented as medical history; abnormal findings thereafter will be documented as AEs (see Section 9.6.1.1).¹⁷⁴

Assessments of Chagas' disease signs and symptoms will be performed at the time of physical examinations (see Section 9.4.4).¹⁷⁵

Part 2 (CHICO SECURE)

Physical examinations will be performed by a medically qualified person. A complete physical examination of body systems will be performed at FU Visit 1, 3, and 5 (see Table 9–2). Abnormal findings on physical examination before signing informed consent will be documented as medical history; abnormal findings thereafter will be documented as AEs (see Section 9.6.1.2). Assessments of Chagas' disease signs and symptoms will be performed at the time of physical examinations.

9.6.3.4 Vitals signs, height/length, and weight

In part 1 of the study, vital signs (systolic and diastolic blood pressure [optional in subjects < 5 years of age at the discretion of the investigator], heart rate, respiratory rate, and oral or rectal body temperature) will be measured at screening and Visits 2, 3, 6, 8 (EOT), 9, 10, and 11. After a 5-minute rest in a sitting position, vital signs will be measured using non-invasive equipment. In part 2 of the study, vital signs (systolic blood pressure, diastolic blood pressure, pulse) will be performed at FU Visits 1, 3, and 5.

Height/length and weight will be obtained with the subject wearing minimal clothing and no shoes.¹⁷⁶

¹⁷³ Text modified/added for clarity (Amendment 1)

¹⁷⁴ Paragraph added per Modification 10 (Amendment 1)

¹⁷⁵ Text added for clarity (Amendment 1)

¹⁷⁶ Text modified to reflect changes made per Amendment 1; last sentence moved from previous section (9.6.3.3) to this section (Amendment 1)

	Integrated Clinical Study Protocol	
	BAY A2502/ 16027	
03 NOV 2020	Version 11.0	Page: 76 of 259

9.6.3.5 12-lead electrocardiogram

A resting 12-lead ECG will be performed at screening and Visits 2, 3, 6, 8 (EOT), and 9, 10, 11 (Follow-up) on all subjects \geq 5 years of age, and at the discretion of the investigator on all subjects < 5 years of age. For subjects consenting to PK assessments, an ECG will be obtained at the 2 – 4 hour time point of PK blood sampling (i.e., at the time of C_{max}), to allow for PK/PD investigations.

The ECG will be performed at the site according to procedure, and with the subject in the supine position after he/she has rested for 10 minutes.¹⁷⁷

A resting 12-lead ECG will be performed at FU Visits 1, 3, and 5 in part 2 of the study on all subjects. The ECG will be performed at the site according to standard procedures, and with the subject in the supine position after he/she has rested for at least 10 minutes.

ECG recordings will be evaluated by the investigator and a cardiologist associated with the site. In case of ECG abnormalities suspicious for cardiac involvement of Chagas' disease, further diagnostic examinations may be required at the discretion of the investigator, (e.g., echocardiography, chest X-ray, 24-hour ECG).

9.6.3.6 Urine pregnancy test

A urine pregnancy test on all female subjects of childbearing potential (i.e., all females who have experienced menarche) will be performed at screening and Visits 2, 3, 6, 8 (EOT), and 9 (Follow-up). If any urine pregnancy test is positive, a serum pregnancy test will be performed to confirm the result. If pregnancy is confirmed at Visits 1 or 2, the subject is to be excluded from study participation. If pregnancy is confirmed at Visits 3 or 6, the subject will be discontinued from the study (See Section 9.6.2) and undergo all study assessments as described for the EOT Visit (Section 9.2.2.7).¹⁷⁸

There will be no urine pregnancy test in part 2 of the study.

9.7 Other procedures and variables

In part 1 of the study, no other procedures will be performed, and no other variables will be measured.

In part 2 of the study, the housing conditions, especially with regard to active or effective vector-control to *T. cruzi* reinfection as determined by Ministry of Health guidelines in each country and the judgement of the investigator, will be inquired at FU Visits 1, 2, 3, 4 and 5.

9.8 Appropriateness of procedures/measurements

The efficacy and safety measurements scheduled for this study are widely used and generally accepted as reliable, accurate, and relevant.

The safety variables evaluated in this study are routine clinical parameters that allow risk assessment of the investigational drug.

¹⁷⁷ Text modified for clarity and per Modifications 1 and 9 (Amendment 1)

 $^{^{178}}$ Text modified/added for clarity and to reflect changes made per Amendment 1

	Integrated Clinical Study Protocol BAY A2502/ 16027	
03 NOV 2020	Version 11.0	Page: 77 of 259

10. Statistical methods and determination of sample size

10.1 General considerations

This study has been designed to focus on the efficacy and safety of treatment with nifurtimox in children diagnosed with Chagas' disease. In this study, approximately 300 pediatric subjects will be randomized (2:1 randomization, 60-day regimen vs. 30-day regimen). Subjects will be stratified by age into four strata. A minimum of 38 subjects in each age stratum is targeted, but not required, in order to be able to derive meaningful safety conclusions. Enrollment will continue until this specification is met, unless it is determined that such a target would be unlikely to be reached in a reasonable time.¹⁷⁹

Unless otherwise specified, all significance tests will be conducted using a 2-sided alpha level of 0.05, and CIs will be 2-sided 95% intervals. All variables collected in this study will be summarized with descriptive statistics at each assessment time. Subject disposition and demographic and baseline characteristics will be summarized descriptively for each treatment group. For continuous variables, descriptive statistics will include means, standard deviations, medians, minimums, and maximums. For categorical variables, frequency counts and percentages will be provided. These will be calculated for each age stratum by dose, as well as the overall set of study subjects.

No imputations will be made for missing values occurring in the safety and background variables. Treatment of missing values for efficacy variables is addressed later in this section.¹⁸⁰ Additional analyses may be specified in the SAP if missing data patterns observed during blinded review of the data suggest any possible bias.

Statistical analysis will be performed using Statistical Analysis System (SAS); the version used will be specified in the SAP.

10.2 Analysis sets

Part 1 (CHICO)

The primary efficacy analysis will be done using the full analysis set (FAS), which is the set of subjects who received at least one dose of study drug. Analyses will also be done using the per-protocol set, which is comprised of subjects treated with study drug who have no major protocol deviations. Complete specifications will be provided in the SAP.

Analyses of safety and background data will be performed on the FAS.

Part 2 (CHICO SECURE)

The primary efficacy analysis will be done using the full analysis set (FAS) as defined in part 1. Subjects will be analyzed as randomized in part 1 (CHICO) of the study. Complete specifications will be provided in the SAP.

¹⁷⁹ Modified as per amendment 2

¹⁸⁰ Text modified/added for clarity (Amendment 1)

	Integrated Clinical Study Protocol BAY A2502/16027	
03 NOV 2020	Version 11.0	Page: 78 of 259

Analyses of safety and background data will be performed on the FAS. For safety analyses, subjects will be analyzed as treated in part 1 of the study.

10.3 Variables and planned statistical analyses

10.3.1 Variables

10.3.1.1 Part 1 (CHICO)

The primary efficacy variable will be sero-reduction or sero-conversion at 12 months post-treatment using two conventional ELISA serology tests as the measure of efficacy. This sero-reduction or sero-conversion is considered cure, and the primary variable is binary (cure, no cure).

In the event of discordancy between the two conventional ELISA test results, the following will be considered:

- For sero-reduction, the average percentage of OD reductions will be used (e.g., Test #1 = 15% and Test #2 = 25%; average = 20% and, hence, cure).
- For sero-conversion, only when both test results are negative the subject is considered as negative (cure).¹⁸¹

Secondary efficacy variables include clinical signs/symptoms of Chagas' disease, concentration test for *T. cruzi* (subjects < 8 months of age at randomization), conventional and non-conventional serologic testing, and disease state determined by qPCR.

Background variables include demographics (sex, age), height/length, weight, medical/surgical history, and medication history.

Safety variables include AEs, physical examination abnormalities, vital signs, ECG abnormalities, hematology and blood chemistry, coagulation, and urinalysis.¹⁸²

10.3.1.2 Part 2 (CHICO SECURE)

Efficacy assessments will be obtained at designated study visits (see Table 9–2).

Primary efficacy variable

The primary efficacy variable will be the incidence rate of seronegative conversion measured and confirmed by two types of assay (recombinant ELISA and IHA) in subjects who were randomized and received at least one dose of the 60-day nifurtimox treatment regimen. Both test results should be negative for the subject to be considered as seroconverted. Incidence rate is the number of new cases of seronegative conversion over the study period (i.e., 4 years after end of nifurtimox treatment) divided by the person-time at risk. [33]

Secondary and other exploratory efficacy variables

Secondary efficacy variables include:

¹⁸¹ Modified as per amendment 2

¹⁸² Text modified/added for clarity and to reflect changes per Amendment 1

Version 11.0

03 NOV 2020

- Incidence rate of seronegative conversion measured and confirmed by two types of assay (recombinant ELISA and IHA) in subjects who were randomized and received at least one dose of the 30-day nifurtimox treatment regimen
- Proportion of responders who show both seronegative conversion by two types of assays and no evidence of established cardiomyopathy as measured by ECG
- Serial reduction of OD measured by recombinant ELISA and total purified antigen ELISA

Other exploratory efficacy variables include:

- Incidence rate of seroconversion measured and confirmed by two types of assay (recombinant ELISA and IHA) in subjects by age categories (≤2 years, >2 years to ≤6 years, >6 to ≤12 years, >12 to <18 years; age is defined as subject's age at randomization)
- Proportion of responders who show seronegative conversion and the incidence rate of seronegative conversion as confirmed by non-conventional serology in subjects who were randomized and received at least one dose of either 60- or 30-day nifurtimox treatment regimens
- Proportion of presence of parasite or positive serology in babies born of mothers who were randomized and received at least one dose of either the 60- or 30-day nifurtimox treatment regimen

Safety variables

Safety variables include AEs and vital signs.

10.3.2 Statistical and analytical plans

10.3.2.1 Part 1 (CHICO)

Efficacy

Primary efficacy analysis

The difference in the proportion of nifurtimox subjects with sero-reduction¹⁸³ or sero-conversion (60-day regimen) and the proportion estimated from historical data will be tested using a 2-sided 95% CI for a single proportion.

The null hypothesis H_0 is $p_{nifurtimox} = p_{placebo}$

The alternative hypothesis H_1 is $p_{nifurtimox} \neq p_{placebo}$, where p_t is the sero-conversion rate for treatment t.

¹⁸³ Text modified for clarity (Amendment 1)

	Integrated Clinical Study Protocol
	BAY A2502/ 16027
03 NOV 2020	Version 11.0

Page: 80 of 259

Superiority will be confirmed if the lower limit of the CI for the proportion of nifurtimox subjects (60-day regimen) with sero-reduction or sero-conversion is greater than the proportion of historical placebo subjects with sero-conversion.¹⁸⁴

Sero-conversion for the historical placebo control is estimated as 16% from cure rates as presented in two publications [15][16], using a number greater than the larger of the upper limits of the 95% CIs from the two studies. Further details about the derivation of these rates are provided in Section 10.4.¹⁸⁵

Secondary and exploratory efficacy analyses ¹⁸⁶

A secondary analysis will be done to compare the proportion of subjects with sero-reduction or sero-conversion for the 60-day and 30-day nifurtimox regimens. This will be performed using a 2-sided 95% CI for the difference of two independent proportions.

The analyses specified above will also be done using data from the EOT visit, and 3 and 6 months after EOT.

The relationship of conventional serology results to qPCR results will be done using frequencies of matches and mismatches on the determination of disease status, and phi-correlation and kappa coefficient to assess the degree of agreement. The relationship of non-conventional serology to conventional serology will be analyzed in the same way.¹⁸⁷ The results from IHA and conventional serology will also be compared. The details of secondary and exploratory efficacy analyses will be further specified in the SAP.^{188,189}

Demographics and baseline characteristics

Demographics and baseline characteristics will be summarized by treatment and total population, using descriptive statistics and frequency tables as appropriate.

Safety

Safety variables will be summarized by means of descriptive statistics and/or frequency tables as appropriate. Summaries will be given by treatment regimen. All post-treatment AEs and SAEs, as well as drug-related AEs and SAEs, will be summarized by MedDRA terms.¹⁹⁰ AEs occurring between the time of consent and the first dose of study drug will be summarized separately. Subjects experiencing urine discoloration from riboflavin ingestion will be listed also, although these incidences will not necessarily be considered AEs.

¹⁸⁴ Text deleted per Modification 2 (Amendment 1)

¹⁸⁵ Text modified as of amendment 2

¹⁸⁶ "Exploratory" added per Amendment 5.

¹⁸⁷ Text modified/added for clarity (Amendment 1)

¹⁸⁸ Sentence added per Amendment 5.

¹⁸⁹ Replaced IFA with IHA per Amendment 6.

¹⁹⁰ Text modified as of amendment 2

03 NOV 2020 Version 11.0

Missing data/drop outs

No imputations will be made for missing data due to dropouts or other causes. For the primary efficacy analysis done on the FAS, a patient without an assessment at the primary 12 month time point will be considered a treatment failure. For the secondary analysis using the PPS, patients who do not have serology determinations to assess the primary endpoint will be excluded from the analysis.

The following sensitivity analyses for the primary efficacy variable will be performed:

• Missing values due to the following reasons treated as treatment failures and other missing values excluded from analysis:¹⁹¹

1. the reason for discontinuation is known or suspected to be treatment ineffectiveness or an AE

2. a subject has not had a negative serology at any visit and has no serology determination for the primary analysis visit

3. an indeterminate or incorrectly performed serology determination occurs at the primary analysis visit.¹⁹²

- Observed data only
- Analysis on PPS

Pharmacokinetic data

Specifications for PK data analysis will be provided in a separate document. Plasma concentration vs time data documented within the study report will be analyzed descriptively using univariate statistics.¹⁹³

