There are several choices for diagnosis of Chagas' disease and monitoring of drug efficacy after anti-parasitic treatment. Traditional parasitological methods, such as direct microscopic observation, xenodiagnoses, and hemoculture, show low sensitivities, limiting their usefulness. Microhematocrit is the method of choice to identify congenital infection because of its heightened sensitivity and the small amount of blood needed. Microscopic examination of cord blood or peripheral blood of the neonate by this technique is strongly recommended during the first month of life. For the monitoring of drug efficacy, the criterion of cure usually depends on serologic conversion of the anti-*T. cruzi* antibody response to negative. Sero-conversion in children and adolescents may occur several years after treatment, requiring long-term follow-up.

Sero-reduction (measured as a $\geq 20\%$ reduction of the ELISA absorbance [OD] value) at 12 months post-treatment will be considered equivalent to historical information on sero-conversion at subsequent time points after treatment.⁷²

Both primary and secondary study endpoints are based upon a target of $\geq 20\%$ decrease in antibody concentration (sero-reduction) to *T. cruzi* in conventional serological tests or negativization of serology. This is consistent with one previous study in children 6 to 12 years of age infected with *T. cruzi* in the intermediate (early chronic) phase of Chagas' disease [15]. Subjects were administered 5mg/kg benznidazole or placebo in a randomized fashion for 60 days, and followed for 48 months. At 12 months, a 21% reduction in concentration of Chagas' disease-specific antibodies compared to baseline (ELISA mean OD 0.467 [± 0.099] vs. 0.369 [± 0.107]) was observed in subjects who received benznidazole. For the subsequent time points of 18, 24, and 48 months, percent concentration reductions in antibody titer were reported as 23%, 29%, and 27%, respectively. After a 48-month follow-up, negative sero-conversion was detected in 11.3% (P<0.05) of the benznidazole group and only 4.5% of the placebo group.⁷³

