The above data are comparable to a study in early chronic Chagas' patients treated with 7.5 mg/kg benznidazole or placebo for 60 days, which also showed approximately 20% antibody concentration reduction at 12 months [16]. Analysis of concentration over time indicated a consistent decrease in antibody concentrations in the benznidazole group, and an initial decrease followed by a progressive increase in the placebo group. At the end of the 3-year follow-up, children who received benznidazole had a significantly lower mean antibody concentration than placebo-treated children (P<0.00001). As persistence of positive results by conventional serology for years after treatment is common, these tests may or may not revert to sero-negative (sero-conversion) after many years or even decades. Thus, reduction in *T. cruzi* antibody concentration has been used in clinical practice as a surrogate indicator for parasitological cure (sero-conversion) following anti-trypanosomal treatment.⁷⁴

While a decrease $\geq 20\%$ in antibody concentration has been demonstrated across two independent clinical trials in pediatric patients with Chagas' disease, neither author has

⁷¹ Text modified for clarity (Amendment 1)

⁷²Text modified for clarity (Amendment 1)

⁷³ Text deleted for clarity as of amendment 2

⁷⁴ Text deleted as of amendment 2

	Integrated Clinical Study Protocol	
	BAY A2502 / 16027	
03 NOV 2020	Version 11.0	Page: 32 of 259

published extended follow-up data which include serological results for the patients in these studies. Since signs and symptoms are usually lacking in early Chagas' disease, it is not possible to demonstrate immediate meaningful clinical benefit to active treatment. However, significant reductions in *T. cruzi* antibody concentration (sero-reduction) by conventional serology has been accepted as a predictor of future sero-conversion, and early treatment cure of infection will ultimately reduce the risk of developing visceral abnormalities, as well as contribute to the decrease in *T. cruzi* transmission.⁷⁵

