Alternative and more rapid approaches as an early indicator of negative sero-conversion in treated patients have been suggested. Using non-conventional serological techniques, i.e., highly sensitive and specific chemiluminescent ELISA using a purified trypomastigote glycoconjugate antigen and an epimastigote complex [20], the time to negativization was significantly sooner for the non-conventional ELISA than for the conventional ELISA. The chemiluminescent ELISAs provide tests that are highly sensitive and specific for Chagas' disease diagnosis. They can be used in blood bank screening and to monitor the treatment of patients undergoing chemotherapy [21].⁷⁶

Non-conventional ELISA antigens, such as those used in the Sosa-Estani and deAndrade trials (i.e., F29 and F 2/3), [15][16] are often considered as early markers for effective Chagas' disease therapy. In the study by Altcheh, et al, the kinetics of disappearance of conventional serology and anti-F2/3 antibodies were compared in 21 patients with congenital Chagas' disease after receiving benznidazole treatment. Patients were divided into two groups: (A) age < 8 months at diagnosis and (B) age > 9 months at diagnosis. Group A presented negative outcome for conventional serology at 6.6 months (CI 95 3.4-9.8 months) and for anti-F2/3 at 4 months (CI 95 0.9-7.1 months, p = 0.18). Group B exhibited nonreactive conventional serology at 63.1 months (CI 95 42.1-84.2 months) whereas anti-F2/3 antibody determination became negative at 21.9 months (CI 95 5.7-38.1 months, p = 0.0025). In patients belonging to Group A, antibodies were undetectable by both conventional serology and anti-F2/3 ELISA soon after receiving chemotherapy. In infants included in Group B, a negative result for anti-F2/3 antibody detection occurred significantly in advance of negative conventional serology reactivity. Consequently, the anti-F2/3 antibody assay becoming negative should be considered as a surrogate endpoint for assessment of cure or positive response to treatment, particularly in those patients with prolonged time of infection [18].

A new perspective on Chagas' disease diagnosis was opened by the use of the PCR as a measure of treatment response. Over the past few years, the availability of PCR to detect *T. cruzi* DNA in blood samples has opened new possibilities for the evaluation of response to trypanocidal chemotherapy.⁷⁷

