10.4 Determination of sample size

Part 1 (CHICO)

This study uses historical controls estimated from cure rates presented in two publications [15][16]. The historical cure rates are as follows.

Publication	Age range	Sero-conversion rate (95%CI) in placebo patients
Andrade et al 1996	7-12	3/65 = 5% (1%,13%)
Sosa et al 1998	6 -12	2/44= 5% (1%,16%)

For the primary objective, superiority over placebo will be confirmed if the lower limit of the 95% CI for the nifurtimox (60-day regimen) cure rate is greater than 16%, the larger of the upper limits of the 95% CIs from the two publications.¹⁹⁴

According to Guhl et al [32], nifurtimox 12 month post treatment cure rate is about 55%, with a sample size of 200 for the 60-day regimen, the power is 99% for the lower limit of the 95% CI to be greater than 16%.¹⁹⁵

The number of subjects in the 30-day treatment regimen is based on the width of a 95% CI for the difference of two proportions. A sample size of 100 subjects for the 30-day subjects together with 200 subjects for the 60-day subjects will produce a CI with a half-width of approximately 0.12.

Part 2 (CHICO SECURE)

¹⁹⁴ Modified as per amendment 2

¹⁹⁵ Modified as per amendment 2

	Integrated Clinical Study Protocol BAY A2502/16027
03 NOV 2020	Version 11.0

Page: 84 of 259

According to Sosa-Estani [15, 35], the 48 months post treatment cure rate for benznidazole is about 5% as confirmed by two types of assay. For the primary objective, assuming a drop-out rate of 15%, the expected number of patients to be observed at the end of Part 2 (i.e., 48 months post treatment) in the 60-day regimen would be 170 out of the 200 patients in Part 1. Using the assumptions of 170 nifurtimox 60-day regimen patients in Part 2, a 5% cure rate, and that seronegative conversion events follow Poisson distribution, the estimated incidence rate is calculated to be 1.32% and the 95% CI of the incidence rate is (0.61%, 1.51%).

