## 6.2 Efficacy

## 6.2.1 Part 1 (CHICO)

## 6.2.1.1 Primary efficacy variable and analysis

The primary efficacy variable will be sero-reduction (defined as  $a \ge 20\%$  reduction in optical density [OD]) or sero-conversion (defined as negative Immunoglobulin G [IgG] concentration) in the 60-day regimen group at 12 months post-treatment using two conventional ELISA serology tests. This sero-reduction (in subjects  $\ge 8$  months to < 18 years of age at randomization) or sero-conversion (in all subjects) is considered cure, and the primary variable is binary (cure, no cure). In the event of discordancy between the two conventional ELISA test results, the following will be considered:

• For sero-reduction, the average percentage of OD reductions for the two conventional ELISA tests will be used (e.g., Test #1 = 15% and Test #2 = 25%; average = 20% and, hence, cure).

BAY No. A2502/IMPACT No. 16027

Page:

- For sero-conversion, only when both test results are negative that the subject is considered as negative (i.e., cure).
- If one of the test results is missing, the subject is considered as "no cure".

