#### Table 6–1: Historical Cure Rates for Placebo

Publication	Age range (in years)	Sero-conversion rate (95%Cl) in placebo patients
de Andrade et al 1996	7-12	3/65 = 5% (1%,13%)
Sosa et al 1998	6 -12	2/44= 5% (1%,16%)

Both publications show a 5% cure rate for the placebo group. For the primary objective in our study, superiority over placebo will be confirmed if the lower limit of the 95% CI for the nifurtimox (60-day regimen) cure rate is greater than 16%, the larger of the upper limits of the 95% CIs from the two publications.

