## Subgroup analyses of the primary efficacy variable

The proportion of nifurtimox subjects with sero-reduction or sero-conversion (60-day regimen) and an asymptotic 2-sided 95% CI for the proportion will be calculated by country and for each age stratum.

The same proportion and an asymptotic 2-sided 95% CI for the difference of the 60-day and 30-day nifurtimox regimens will also be summarized by country and for each age stratum.

BAY No. A2502/IMPACT No. 16027

Page:

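### The 16% bar for Part 1 superiority comes from sero-conversion in placebo children aged 6 to 12, but is applied to a pooled 0 to 17-year composite that it is not shown to bound

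*Protocol*

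**What the plan says.** Protocol 10.3.2.1 confirms superiority when the lower confidence limit for the 60-day proportion "with sero-reduction or sero-conversion is greater than the proportion of historical placebo subjects with sero-conversion". Protocol 10.4 fixes the bar at "greater than 16%, the larger of the upper limits of the 95% CIs from the two publications". The sources are 3/65 placebo children aged 7 to 12 and 2/44 aged 6 to 12. Below its Table 6–1 the SAP adds: "Both publications show a 5% cure rate for the placebo group". Protocol 5.1 puts follow-up in those trials at 4 and 3 years.

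SAP 6.2.1.1 counts a fall in optical density of at least 20% as cure from 8 months of age, "or sero-conversion (in all subjects) is considered cure, and the primary variable is binary". Sero-conversion means that both conventional ELISAs are negative at 12 months; baseline status is not mentioned. Under Protocol 6.1, subjects under 8 months enter on direct sight of the parasite and need no positive ELISA. From 8 months, two positive ELISAs, or documentation of them, are needed.

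Protocol 5.1 bridges the two endpoints by stating that 12-month sero-reduction "will be considered equivalent to historical information on sero-conversion at subsequent time points after treatment". It also reports, in one of the control trials, "an initial decrease followed by a progressive increase in the placebo group".

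**The concern.** The control and the tested quantity differ in three ways.

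- **Age.** No untreated rate is given below 6 or above 12 years. The protocol expects age to matter: in a small benznidazole-treated series of congenital cases it cites, "Group A presented negative outcome for conventional serology at 6.6 months", against 63.1 months in the group diagnosed later (Group A was under 8 months of age at diagnosis, Group B over 9 months).
- **Endpoint.** No untreated rate is given for a 20% fall in optical density. The equivalence in Protocol 5.1 is declared rather than estimated, and antibody did fall at first on placebo. The size and timing of that fall are not reported.
- **Baseline.** A subject under 8 months who is ELISA-negative at Visit 1 and still negative at 12 months scores as converted.

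At stake is what a single superiority statement for ages 0 to 17 means. It could rest largely on an age group absent from the control, or on an endpoint component the control did not measure.

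**Working it through.** **1. The plan's own figures.** Exact 95% limits are 1.0% to 12.9% for 3/65 and 0.6% to 15.5% for 2/44; the larger upper limit rounds to 16%. The SAP's lower limit is p − 1.96√(p(1−p)/n) − 1/(2n). With the protocol's n = 200:

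- 44 cures: 0.22 − 1.96 × 0.02929 − 0.0025 = 0.1601, a pass.
- 43 cures: 0.1556, a fail.

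At the planned 55% cure rate, P(at least 44 of 200) exceeds 99.9%, so the stated 99% power holds. At a true pooled rate of exactly 16% the pass chance is 1.6%. The arithmetic is sound; the question is what 16% represents.

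**2. Control against test.**

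| | Control behind 16% | Part 1 primary analysis |
|---|---|---|
| Age | 6 to 12 years | 0 days to under 18 years, pooled |
| Endpoint | sero-conversion | sero-conversion, or sero-reduction from 8 months of age |
| Time | 3 to 4 years | 12 months |

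**3. How far subjects under 8 months could drive the result.** Strata 1 and 2 at the target of 38 each give 76 × 2/3 = 50.7, or 51 on 60 days; 40 and 27 are tried as lower enrolments. Let k be their number, π their conversion rate, and 5% the cure rate in the other 200 − k. The pass chance is P(Bin(k, π) + Bin(200 − k, 0.05) ≥ 44):

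| k | π = 50% | 60% | 70% | 80% | 85% |
|---|---|---|---|---|---|
| 51 | 1% | 11% | 47% | 89% | 98% |
| 40 | <0.1% | 0.3% | 3% | 17% | 33% |
| 27 | <0.1% | <0.1% | <0.1% | <0.1% | <0.1% |

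All values of k and π, and the 5%, are assumptions. For k = 51 and π = 80% the true pooled rate is (51 × 0.80 + 149 × 0.05)/200 = 24.1%. Each baseline-negative subject scored as cured adds 1/200 = 0.5 percentage point.

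**4. The endpoint gap.** If the untreated composite rate were 20% or 25%, a drug with no effect would pass with probability 26% or 86% (P(Bin(200, p) ≥ 44)). The documents give no value, so these rates are illustrative.

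**5. A supporting analysis from 8 months of age.** With 200 − 51 = 149 subjects, 35 cures pass: 0.2349 − 1.96 × 0.03473 − 1/298 = 0.1635 (34 give 0.1574). Power is 69% at a true 25%, 97% at 30% and above 99.9% at 55%.

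**The case against.** The bar has real strengths. It is an upper limit placed over a 5% estimate, and it sets 3 to 4 years of placebo conversion against 12 months. For sero-conversion alone at ages 6 to 12 it is conservative. Protocol 5.1 explains that a placebo arm would be unethical and that only two placebo-controlled paediatric trials exist, so the plan may have no matched infant control to use.

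Other outputs help. The SAP's subgroup section says the 60-day rate with a "2-sided 95% CI for the proportion will be calculated by country and for each age stratum", so stratum 4 (2 to under 18 years) can be read without infants. SAP 6.1.2 summarises baseline ELISA by age stratum. Table 6–2 separates sero-negative from sero-reduction, within the comparison with IHA. Part 2 tests sero-negative conversion alone over 4 years and reports it by age category, including over 6 to 12 years. These mitigate part of the gap. None carries the 16% criterion outside the pooled set, combines strata 3 and 4, or links baseline serology to cure.

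Three stronger readings are tempting and are not supported:

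- **That the rule inflates type I error.** In the scenario with 51 infants at 80%, the true pooled rate is 24.1%, so passing is correct for the hypothesis as stated.
- **That 16% lies below the untreated rate.** The documents give no untreated rate for sero-reduction or for infants, so it is only not shown to bound them.
- **That a baseline-negative infant is a treatment failure.** Entry rests on a seen parasite, and no passage supports scoring such a child as a failure. In the cited series, treated infants became negative at 6.6 months, which suggests that most were positive first.

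**Conclusion.** The point holds as a limit on interpretation, with a cheap remedy. The 16% bar matches neither the full age range nor the composite endpoint, and it is not shown to bound the untreated composite rate.

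Infants can dominate the pooled result only under two conditions together: enrolment near a target that the protocol says is not required, and high 12-month conversion. At 80% conversion, with older children at 5%, the pass chance falls from 89% to 17% to below 0.1% as infants fall from 51 to 40 to 27. The 5% is itself pessimistic beside the planned 55%. The 60% to 85% early-phase figure in the protocol's benefit-risk section is parasitological cure and cannot be read as 12-month sero-conversion; missing results also count as failures. How many subjects under 8 months are ELISA-negative at baseline cannot be learned from the documents.

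**What to change.** Leave the pooled primary endpoint and its pass/fail rule unchanged, and add to the SAP:

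- **(a) Supporting analysis.** The 60-day cure rate in subjects aged 8 months or older at randomization, with the same 95% interval read against 16%. Show ages 6 to 12 descriptively as the closest match to the control, and show sero-conversion and sero-reduction separately beside the composite.
- **(b) Sensitivity analysis, subjects under 8 months only.** Exclude, as non-evaluable for sero-conversion, those whose stored Visit 1 sample was not positive on both ELISAs, and report their number.
- **(c) Statement of scope.** The historical control directly supports superiority only for the ages and endpoint it covers; results under 8 months have no matched untreated control; and 16% has not been shown to bound the untreated 12-month sero-reduction rate.

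If Part 1 is already unblinded, label all of these supplementary; the documents do not give its status.

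The cost is SAP wording and a few tables, from data and stored samples already planned. The supporting set is smaller: about 149 subjects if both infant strata reach target, with the power shown above. It still includes ages 8 months to 5 years and 13 to 17, which the control does not cover, and it does not resolve the sero-reduction gap; that is why (c) is needed.
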